### **6.2.2. Drugs That May Have Their Plasma Concentrations Altered by Ibrutinib**

In vitro studies indicated that ibrutinib is not a substrate of P-glycoprotein (P-gp), but is a mild inhibitor (with an IC50 of 2.15 µg/mL). Ibrutinib is not expected to have systemic drug-drug interactions with P-gp substrates. However, it cannot be excluded that ibrutinib could inhibit intestinal P-gp after a therapeutic dose. There is no clinical data available; therefore, to avoid a potential interaction in the GI tract, narrow therapeutic range P-gp substrates such as digoxin, should be taken at least 6 hours before or after ibrutinib.

### **6.2.3. QT Prolonging Agents**

Any medications known to cause QT prolongation should be used with caution; periodic ECG and electrolyte monitoring should be considered

For a list of potential medications which may prolong the QT interval please review the following link. If there are additional questions/concerns contact the P.I. [name] or [name].

[www.rettsyndrome.eu/wp-content/uploads/2015/10/CombinedList.pdf](http://www.rettsyndrome.eu/wp-content/uploads/2015/10/CombinedList.pdf)

### **6.2.4 Antiplatelet Agents and Anticoagulants**

Use ibrutinib with caution in subjects requiring other anticoagulants or medications that inhibit platelet function. In an in vitro platelet function study, inhibitory effects of ibrutinib on collagen-induced platelet aggregation were observed. Supplements such as fish oil and vitamin E preparations should be avoided during treatment with ibrutinib. Bleeding events of any grade, including bruising and petechiae, occurred in subjects treated with ibrutinib. Subjects with congenital bleeding diathesis have not been studied. Ibrutinib should be held at least 3 to 7 days pre- and post-surgery depending upon the type of surgery and the risk of bleeding (see Section 6.3).

### **6.3. Prohibited Concomitant Medications**

Any chemotherapy, anticancer immunotherapy, experimental therapy, or radiotherapy are prohibited while the subject is receiving ibrutinib treatment.

Corticosteroids for the treatment of the underlying disease are prohibited. Corticosteroids for the treatment of non-cancer related reasons for longer than 14 days and/or at doses >100mg of prednisone or its equivalent are prohibited.

*Erythropoietic growth factors (eg, erythropoietin) and neutrophil growth factors (eg, filgrastim and peg-filgrastim) are also prohibited during the initial cycle (28 days) of treatment*

## **6.4 Guidelines for Ibrutinib Management with Surgeries or Procedure**

Ibrutinib may increase risk of bleeding with invasive procedures or surgery. The following guidance should be applied to the use of ibrutinib in the perioperative period for subjects who require surgical intervention or an invasive procedure while receiving ibrutinib:

### **6.4.1. Minor Surgical Procedures**

For minor procedures (such as a central line placement, skin or needle biopsy, thoracentesis, or paracentesis) ibrutinib should be held for at least 3 days prior to the procedure and should not be restarted for at least 3 days after the procedure. For bone marrow biopsies that are performed while the subject is on ibrutinib, it is not necessary to hold ibrutinib.

### **6.4.2. Major Surgical Procedures**

For any surgery or invasive procedure requiring sutures or staples for closure, ibrutinib should be held at least 7 days prior to the intervention (except for emergency procedures) and should be held at least 7 days after the procedure and restarted at the discretion of the investigator when the surgical site is reasonably healed without serosanguinous drainage or the need for drainage tubes.

## **7. STUDY EVALUATIONS**

### **7.1 Description of Procedures**

The study is divided into 3 phases: a Screening Phase, a Treatment Phase, and a Post treatment Phase. Screening occurs from the time of informed consent up to commencement of therapy on cycle 1 day 1. Treatment includes the time frame from commencement of therapy including the end of treatment visit. The post treatment phase includes the time from end of treatment until progression, death or next therapy. During the Post treatment Phase, subjects will be followed for survival and subsequent anti-HL therapy until death, withdrawal of consent, confirmed lost to follow-up, or the end of study, whichever occurs first.

#### **7.1.1. Assessments**

- **Screening phase**
  - All patients must sign an informed consent prior to any study related procedures listed below with the exception of CT or PET imaging which can be performed prior to informed consent if done within 28 days of Day 1 of therapy.

- Screening procedures will be performed up to 28 days before first dose of study drug. Subjects must satisfy all of the inclusion and none of the exclusion criteria listed in Section 4.1 and Section 4.2, respectively, before receiving the first dose of study drug. The results of laboratory tests noted in the inclusion criteria must be within the limits specified prior to the first dose of study drug. Testing can be repeated for this purpose. The last result obtained prior to start of study treatment will be used to determine eligibility
- During the Screening Phase, eligibility criteria will be reviewed and a complete clinical evaluation will be performed (Appendix 1). A complete medical history and physical exam (including concomitant medications, vital signs, height, and weight) with baseline evaluation of lymphoma B-symptoms, adverse events and ECOG performance status (**See appendix 2**) will be conducted.
- 12 lead ECG
- All subjects must undergo a whole body FDG-PET scan and CT scan with contrast. Evaluation of other sites of disease, as relevant, may be performed. In instances where contrast cannot be utilized a discussion with the principal investigator is necessary.
- Laboratory studies including CBC with differential, Serum chemistries, hepatitis serologies, coagulation panels (**See Appendix 1**)
- Correlative biomarker analysis MUST be drawn prior to dose on cycle 1 day 1 of therapy (**See Lab Manual**)
- **A fresh tissue biopsy (excisional lymph node biopsy) is highly recommended for correlative analysis. In instances where an excisional lymph node biopsy is not obtainable, core needle biopsy (4 cores minimum) is recommended.**
- If fresh tumor biopsy is unobtainable, a formalin-fixed paraffin embedded (FFPE) tumor block must be submitted for correlative analysis. (**See Lab Manual**) For screening, a report confirming the diagnosis of Hodgkin's lymphoma is required.
- Subjects must initiate ibrutinib treatment within 28 days of the start of the screening phase
- **Treatment Phase**
  - Throughout the Treatment Phase, the investigator will assess subject response to therapy using efficacy measurements and disease response criteria. Subjects will be monitored for safety, and adverse event information will be collected using the National Cancer Institute Common Terminology Criteria for Adverse Events (NCI-CTCAE) Version 4.03. Dose modifications will be made as required according to dose-modification rules (Section 5.4). The frequency of study procedures and assessment to be conducted during the Treatment Phase are outlined in Appendix 1. However, clinical evaluations and laboratory studies may be repeated more frequently if clinically indicated
  - During each Day one of therapy a symptom-directed physical exam (including lymphoma B-symptoms and performance status will be conducted and the results of all laboratory tests will be reviewed. Adverse events and changes to concomitant medications will be recorded (**see Section 6 for concomitant medications**). Subjects will be evaluated throughout the Treatment Phase for possible toxicities, and modifications in dosing will be made as required according to the criteria in Section

3. The investigator will assess subject response to therapy using the efficacy measurements and disease response criteria according to the schedule described the study calendar (**See Appendix 1 notation g and i**). For subjects who remain on study treatment beyond 15 months from the date of enrollment, site visits may be conducted every 56 days.

- Subjects will be issued diary cards to record study drug dosing. Instructions for proper self-administration and study drug storage conditions will be provided. Precaution associated with the use of study drug and prohibited concomitant medications will be reviewed. The investigator or designated study research staff will review the study diary at the beginning of each cycle and provide additional instruction to re-educate any patient who has not followed the study treatment schedule. Patients on study should refrain from taking the study drug on the morning of study visits designated for commencement of a new cycle until seen at the site. When all evaluations have been completed, and it has been determined that the subject can continue treatment, ibrutinib capsules for 1 cycle of treatment will be dispensed.
- Treatment will continue until progressive disease or unacceptable toxicity occurs. If progressive disease is diagnosed the subject will discontinue study drug, complete the End of Treatment Visit within 30 days, and enter the Post treatment Phase.
- To assess ibrutinib's influence on T cell behavior and antitumor effect, serial serum samples pre and post therapy will be assessed for Th1 ( (IFN- $\gamma$ ) and Th2 cytokines (IL-10, IL-4 and IL-13) at 4 distinct time points (pre-dose cycle 1 day one, cycle 1 day 2 , cycle 1 day 15) , and cycle 2 day 1 (**See Appendix 1**). All assessments will occur prior to dosing that day. **Patients must be instructed not to swallow study drug prior to biomarker evaluation on cycle 1 day 1, cycle 1 day 2, cycle 1 day 15, and cycle 2 day 1.**
- An End of Treatment Visit will be scheduled within 30 days after the last dose of study drug for all subjects, including those discontinuing treatment for any reason, except for those lost to follow-up, death, or withdrawal of consent for study participation. Subjects who discontinued from treatment (due to progression, adverse event, or other reasons) and enter the Posttreatment Phase should have the End of Treatment Visit completed before starting any subsequent anti-HL treatment. If a subject is unable to return to the site for the End of Treatment Visit, the subject should be contacted to collect adverse events that occur within 30 days after the last dose of study drug.

- **Follow Up Phase**
  - The Posttreatment Phase is the time between the End of Treatment Visit and end of study participation or the end of study. The clinical cutoff for primary analysis will occur approximately 1 year after the last subject is enrolled. Investigators will be informed of the timing of the clinical cutoff. It is imperative that the regularly scheduled disease assessments (clinical and radiographic) are performed throughout the Posttreatment Phase for subjects who discontinue treatment prior to disease progression, as outlined in Section 7.3.1 Evidence of clinical relapse according to the Revised Response Criteria for Malignant Lymphoma is to be documented at the time at which it is first detected. During this period, assessments will be performed until

disease progression, death or study end, whichever comes first. Subjects off treatment will be contacted every 9 weeks to obtain data on subsequent anti-HL therapies (including treatment regimen, start date, end date, and best response to subsequent therapy) and survival status. If the information on subsequent anti-HL therapies and survival status is obtained via telephone contact, written documentation of the communication must be available for review in the source documents. If the subject has died, the date and cause of death will be collected and documented on the CRF.

### 7.1.2. Pharmacokinetics/Biomarkers

- To assess ibrutinib's influence on T cell behavior and antitumor effect, serial serum samples pre and post therapy will be assessed for Th1 ( (IFN- $\gamma$  ) and Th2 cytokines ( IL-10, IL-4 and IL-13) at 4 distinct time points (pre-dose cycle 1 day one, pre-dose cycle 1 day 2 , pre-dose cycle 1 day 15) , and pre-dose cycle 2 day 1 (See **Appendix 1**). All assessments will occur prior to dosing that day.

## 7.2.0 Efficacy Evaluations

The investigator will perform tests that will allow evaluation of response to therapy according to the Revised Response Criteria for Malignant Lymphoma. An evaluable patient will be defined as “any patient receiving study drug for > 1 cycle and having completed at least one radiographic (CT with contrast or PET) evaluation. Patients missing > 25% (14 doses) of study drug prior to the initial study evaluation (cycle 3 day 1 +/- 7days) will not be evaluable for efficacy but may remain on study pending a discussion with the medical monitors [name] or [name]. Efficacy assessments will be performed as outlined in **Appendix 1** and **Section 7.3**. These assessments are to be conducted until disease progression, withdrawal of consent from study participation, or the end of study. For subjects who discontinue study drug before disease progression is documented, disease assessments will continue in the Posttreatment Phase. The determination of disease status for continuation of treatment will be assessed by the investigator based on the results of the efficacy assessments. For all subjects, documentation of disease progression must be sent within 24 hours to the sponsor's medical monitor.

## 7.3 Evaluations

### 7.3.1 Radiographic Image Assessments

During the study, disease response will be assessed using whole body FDG-PET scans and CT scans with IV contrast of the neck, chest, abdomen, and pelvis and any other location where disease was present at screening. Subjects who are intolerant of IV CT contrast agents will have CT scans performed with oral contrast. A separate CT scan and PET scan are preferred but, if the only available modality is combined/dual PET/CT scanner, then the CT portion of a PET/CT may be performed in lieu of a dedicated CT; however, the CT scanning must be done with contrast 1 to ensure that an optimized CT examination is done. Evaluation of other sites of disease by radiological imaging, physical examination, or other procedures as necessary (to be performed throughout the study using the same method of assessment used to assess disease at

baseline), and review of hematology and clinical chemistry results may be performed at the site level, as determined by the investigator. Magnetic resonance imaging may be used to evaluate sites of disease that cannot be adequately imaged using CT (in cases where MRI is desirable, the MRI must be obtained at baseline and at all subsequent response evaluations). For all other sites of disease, MRI studies do not replace the required neck, chest, abdomen, and pelvic CT scans. Brain MRI and lumbar puncture are required, only if clinically indicated.

Radiological assessments will be performed at Screening, (PET and CT w/ contrast) upon completion of cycle 2 (week 8 PET and CT w/ contrast). Thereafter, CT with contrast will be performed every 12 weeks until disease progression, death, or end of study, whichever comes first. Patients who remain on study without progression at 15 mos. may have subsequent imaging performed every 24 weeks. A PET scan will be performed at Screening and after cycle 2 and at CR. PET scans will also be done at the time of maximal tumor reduction (eg, CR or 2 consecutive CT scans showing no further tumor reduction), relapse from CR, and at suspected disease progression if new lesion was detected on CT.

Subjects who discontinue treatment prior to disease progression (for other reasons such as an adverse event) must continue to have regularly scheduled CT scans/efficacy assessments every 12 weeks up to 15 months after the start of study drug. Thereafter, scan will be performed every 24 weeks until disease progression, or death, or the end of the study, whichever occurs first. It is important that instances of progressive disease be reported to the lead investigators at Karmanos Cancer Institute within 24 hours by means of the tumor response form provided at site initiation.

### **7.3.2. Positron Emission Tomography (PET)**

PET using [18F]-fluorodeoxyglucose (FDG) is important for the complete assessment of response and progression in subjects with HL. Whole body FDG-PET scan (skull base to the proximal femur) should be done at Screening, After 2 cycles of therapy ( week 8), at the time of maximal tumor reduction (eg, CR or 2 consecutive CT scans showing no further tumor reduction), relapse from CR, and at suspected disease progression if new lesion was detected on CT.

Assessment of PET results is based on published criteria. Visual assessment is considered adequate for determining whether a PET scan is positive, and use of the standardized uptake value is not necessary. A positive scan is defined as focal or diffuse FDG uptake above background in a location incompatible with normal anatomy or physiology, without a specific standardized uptake value cutoff. Other causes of false-positive scans should be ruled out.

Exceptions include mild and diffusely increased FDG uptake at the site of moderate- or large sized masses with an intensity that is lower than or equal to the mediastinal blood pool, hepatic or splenic nodules 1.5 cm with FDG uptake lower than the surrounding liver/spleen uptake, and diffusely increased bone marrow uptake within weeks after treatment.

### **7.3.3 Definition of Measurable and Assessable Disease**

Eligible subjects must have at least 1 measurable site of disease. Measurable sites of disease are defined as lymph nodes, lymph node masses, or extranodal sites of lymphoma. Each measurable site of disease must be greater than 1.5 cm in the short axis regardless of long axis measurement, and clearly measurable in 2 perpendicular dimensions. Measurement must be determined by imaging evaluation. All other sites of disease are considered assessable, but not measurable.

Up to 6 measurable sites of disease, clearly measurable in 2 perpendicular dimensions, will be followed for each subject. Measurable sites of disease should be chosen such that they are representative of the subject's disease (this includes splenic and extranodal disease). If there are lymph nodes or lymph node masses in the mediastinum or retroperitoneum larger than 1.5 cm in 2 perpendicular dimensions, at least 1 lymph node mass from each region should always be included. In addition, selection of measurable lesions should be from as disparate regions of the body as possible and PET avid.

All other sites of disease will be considered assessable. Assessable disease includes objective evidence of disease that is identified by radiological imaging, physical examination, or other procedures as necessary, but is not measurable as defined above. Examples of assessable disease include bone lesions; mucosal lesions in the GI tract; effusions; pleural, peritoneal, or bowel wall thickening; disease limited to bone marrow; and groups of lymph nodes that are not measurable but are thought to represent lymphoma. In addition, if more than 6 sites of disease are measurable, these other sites of measurable disease may be included as assessable disease.

#### **7.3.4. Bone Marrow Assessment**

Bone marrow aspirate and biopsy are optional at screening and based on investigator's clinical judgment. However, if there is evidence of marrow involvement at screening, a repeat bone marrow evaluation must be performed at the time of CR to confirm remission. This must be done within 30 days of initial documentation of CR.

#### **7.3.5 Criteria for Response Categories**

The response categories being used to assess efficacy are based on the Revised Response Criteria for Malignant Lymphoma. (See Appendix 4)

##### **Complete Response**

For CR determination, all the following criteria must be met:

1. Complete disappearance of all detectable evidence of disease and disease-related symptoms.
2. All lymph nodes and nodal masses must have regressed on CT to normal size (equal to or smaller than 1.5 cm in the greatest transverse diameter [GTD] for nodes greater than 1.5 cm before therapy, regardless of the short axis). Previously involved nodes that were between 1.1 cm and 1.5 cm in the long axis and more than 1.1 cm in the short axis before treatment must have decreased to or be equal to 1 cm in the short

axis after treatment. All splenic and hepatic nodules and other extranodal disease must have disappeared.

3. PET scan must be negative (for the combined CT+PET assessment of CR). A posttreatment residual mass of any size is permitted as long as it is PET-negative.
4. The spleen and/or liver, if enlarged before therapy on the basis of physical examination or CT scan, should not be palpable on physical examination and should be considered normal size by imaging studies.
5. If bone marrow was involved before treatment, the infiltrate must have cleared on repeated bone marrow biopsy. If a sample is intermediate by morphology, it should be negative by IHC (if bone marrow was involved before therapy and a radiological CR was achieved, but with no bone marrow assessment after treatment, the response should be classified as a PR.)
6. No new sites of disease are detected during assessment.

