### **Partial Response**

For PR determination, all the following criteria must be met:

1. 1. A  $\geq 50\%$  decrease in the sum of the product of the diameters (SPD) of up to 6 of the largest dominant nodes or nodal masses.
2. No increase should be observed in the size of other nodes, liver, or spleen, meeting the criteria for progressive disease.
3. Splenic and hepatic nodules must regress by  $\geq 50\%$  in the SPD or, for single nodules, in the GTD.
4. With the exception of splenic and hepatic nodules, other organs should not have any measurable disease.
5. Bone marrow assessment is not required for PR determination.
6. No new sites of disease should be observed.
7. At least 1 PET-positive site of disease (required for the CT+PET assessment of PR).

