### **Stable Disease**

1. A subject is considered to have stable disease when he or she fails to attain the criteria needed for a CR or PR, but does not fulfill those for progressive disease.
2. The PET should be positive at 1 or more previously involved sites of disease, with no new areas of lymphoma involvement on the posttreatment CT or PET (for the combined CT+PET assessment of stable disease).

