## Appendix 4. Response Criteria

### Revised response criteria for lymphoma

Response criteria	PET-CT-based response	CT-based response
Complete remission (CR)		
Lymph nodes and extralymphatic sites	Score 1, 2, or 3* with or without a residual mass on 5-PS**  No extralymphatic sites of disease	Target nodes/nodal masses must regress to $\leq 1.5$ cm in LD i
Non-measured lesion Organ enlargement New lesions Bone marrow	Not applicable Not applicable None No evidence of FDG-avid disease in marrow	Absent Regress to normal None Normal by morphology; if indeterminate, IHC negative
Partial remission (PR)		
Lymph nodes and extralymphatic sites	Score 4 or 5** with reduced uptake compared with baseline and residual mass(es) of any size	$\geq 50\%$ decrease in SPD of up to 6 target measurable nodes and extranodal sites
Organ enlargement New lesions Bone marrow	Not applicable  None Residual uptake higher than uptake in normal marrow but reduced compared with baseline (diffuse uptake compatible with reactive changes from chemotherapy allowed). If there are persistent focal changes in the marrow in the context of a nodal response, consideration should be given to further evaluation with MRI or biopsy, or an interval scan	Spleen must have regressed by $>50\%$ in length beyond normal None Not applicable
No response or stable disease (SD)		
Target nodes/nodal masses, extranodal lesions	No response: score 4 or 5 with no significant change in FDG uptake from baseline, at interim or end of treatment	Stable disease: $<50\%$ decrease from baseline in SPD of up to 6 dominant, measurable nodes and extranodal sites; no criteria for PD are met
Non-measured lesions Organ enlargement New lesions Bone marrow	Not applicable Not applicable None No change from baseline	No increase consistent with progression No increase consistent with progression None Not applicable

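### Section 7.3.5 contradicts itself on PET-negative residual masses, and no text says which reading decides the ORR

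*Combined protocol and SAP*

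**What the plan says.** The primary endpoint is the ORR, the proportion of participants with CR or PR (Section 9.3.1). Section 7.3.5 defines the categories. It says "The response categories being used to assess efficacy are based on the Revised Response Criteria for Malignant Lymphoma" and points to Appendix 4.

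- **CR.** The list opens with "For CR determination, all the following criteria must be met". Item 1 requires all detectable disease to be gone. Item 2 states "All lymph nodes and nodal masses must have regressed on CT to normal size"; a node above 1.5 cm at baseline must be 1.5 cm or less. Item 3 requires a negative PET and adds "A posttreatment residual mass of any size is permitted as long as it is PET-negative".
- **PR.** Item 1 needs a fall of at least 50% in the sum of the products of the diameters (SPD). Item 7 adds "At least 1 PET-positive site of disease (required for the CT+PET assessment of PR").
- **SD.** Item 1 is a default for anyone who "fails to attain the criteria needed for a CR or PR, but does not fulfill those for progressive disease". Item 2 says "The PET should be positive at 1 or more previously involved sites of disease", limited in its own text to the combined CT+PET assessment.
- **Appendix 4.** It has two columns. The PET-CT column gives CR for a score of 1 to 3 "with or without a residual mass on 5-PS". The CT-based column classifies by size.

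**The concern.** Every patient enters with FDG-avid, measurable disease (Section 4.1). A PET that turns negative over a mass that has not fully shrunk is therefore a result the criteria must be able to score. PET and CT are both scheduled after cycle 2 (Section 7.3.1), so the combined assessment is the planned one at the first response evaluation.

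CR items 2 and 3 cannot both bind such a patient when all items must be met, and neither refers to the other. Item 1 has the same tension with item 3. PR item 7 and SD item 2 then leave no clean category to fall back on.

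Response is judged by the investigator (Sections 7.1.1 and 7.2.0) at 4 institutions (Section 9.6), and no central review of response is described. If sites resolve the clash differently, the sole primary endpoint does not mean the same thing everywhere. With a cut-off of 13 of 31, a change in one or two patients matters.

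**Working it through.** **Step 1: classify one patient under each available reading.** The patient is PET-negative, has a node still above 1.5 cm, has no new or growing lesion (so is not progressive), and meets the other items of the category concerned.

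| Reading | SPD down 50% or more | SPD down less than 50% |
|---|---|---|
| (a) 7.3.5 literal, CT+PET | Not CR (item 2), not PR (item 7); SD at best by SD item 1, against SD item 2 | Same, and PR item 1 also fails |
| (b) 7.3.5, item 3 as an exception to item 2 | CR | CR |
| (c) 7.3.5, CT alone | PR | SD |
| (d) Appendix 4, PET-CT column | CR | CR |
| (e) Appendix 4, CT-based column | PR | SD |

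With SPD down by 50% or more, the patient is a responder under (b) to (e) and not under (a). With SPD down by less than 50%, the patient is a responder under (b) and (d) and not under (a), (c) or (e). In that second case, ORR status changes even between the readings that avoid the literal clash.

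Under (a) the patient still counts in the denominator. Section 9.2 defines evaluability by cycles completed, imaging done and doses taken, not by having an assigned category.

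**Step 2: reproduce the design.** Inputs from the synopsis and Section 9.5 are n = 31, rejection at 13 or more, p0 = 30% and pA = 50%. Exact binomial tails give:

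- Type I error = P(Bin(31, 0.30) ≥ 13) = 0.1069, matching the stated 10.69%.
- Power = P(Bin(31, 0.50) ≥ 13) = 0.859, against the stated 85%.

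**Step 3: illustrate what under-counting would do.** Let f be the share of true responders who are PET-negative with a residual node and are scored as non-responders. The documents give no value for f, so 5% to 30% is an assumption. The calculation also assumes that every site uses reading (a).

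Power = P(Bin(31, 0.50 × (1 − f)) ≥ 13); type I error = P(Bin(31, 0.30 × (1 − f)) ≥ 13).

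| f | Effective ORR if true ORR is 50% | Power | Type I error |
|---|---|---|---|
| 0 | 50% | 85.9% | 10.7% |
| 5% | 47.5% | 78.8% | 7.6% |
| 10% | 45% | 69.8% | 5.2% |
| 20% | 40% | 48.0% | 2.1% |
| 30% | 35% | 26.4% | 0.7% |

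In patient counts, losing exactly one true responder raises the effective cut-off to 14: P(Bin(31, 0.50) ≥ 14) = 76.3%. Losing two gives P(Bin(31, 0.50) ≥ 15) = 64.0%.

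**The case against.** A reader might infer that a PET-negative patient with a residual mass necessarily fits no category and drops out of the ORR numerator. The documents do not support that, for four reasons.

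1. The permissive sentence in CR item 3 has no work to do unless it relaxes item 2. Reading it as an exception is natural, and it explains why PR and SD ask for PET positivity: PET-negative patients would already be CR.
2. PR item 7 and SD item 2 are each limited to the combined CT+PET assessment. After week 8 the routine scan is CT every 12 weeks, with PET only at specified events. On CT alone a patient with a large enough SPD fall is PR.
3. SD item 1 is a default, so having no category at all is contestable.
4. Section 7.3.5 sends the reader to Appendix 4, whose PET-CT column classes this patient as CR.

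These points stand as far as they go: with SPD down by 50% or more, only the literal reading loses the patient. They do not remove the problem. The exception is implied, not written. The combined assessment is exactly what is planned at week 8. The SD default takes the patient out of ORR anyway and conflicts with SD item 2. Appendix 4 has two columns, and neither it nor Section 7.3.5 says which governs. Below a 50% SPD fall, the readings split between CR and SD.

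**Conclusion.** Section 7.3.5 is internally inconsistent on PET-negative residual masses, and the plan does not say which text, or which column of Appendix 4, determines ORR. That much rests on the wording alone. Loss of these patients from the numerator is one possible result, not an established one. Inconsistent scoring between sites is the more secure worry.

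The size is unknown. It would be wrong to read the table as a forecast that power falls to 26%: f is assumed, and uniform literal application is assumed too. If responders were under-counted, the error would be conservative for a false positive claim and would cost power to detect real activity. If the wording is reconciled so that these patients count as responders, the design keeps its 10.7% type I error and 85.9% power. The point should be settled before responses are classified.

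**What to change.** - Reword CR item 2 so that nodes and masses must return to normal size on CT unless what remains is PET-negative, in which case its size does not matter (item 3).
- Align CR item 1 with that exception.
- State that, on this point, Section 7.3.5 agrees with the PET-CT column of Appendix 4, and that the PET-CT assessment governs ORR when both scans are available.
- Check PR item 7 and SD item 2 against the new wording so that each scan result falls in exactly one category. Two cases to test are a PET-negative patient whom CR item 5 sends to PR for want of a repeat marrow, which PR item 7 now blocks, and a PET-negative patient whose spleen is still enlarged (CR item 4).
- State which definition of PET-negative applies: Section 7.3.2 uses a visual positive or negative reading, while Appendix 4 uses a five-point score.

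Deleting CR item 3 would not be a sound alternative. It would remove the requirement for a negative PET, although Section 3.1 requires PET imaging to document CR. It would also leave SD item 2 in place, so a PET-negative patient with an SPD fall below 50% would still have no clean category.

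The cost is a short edit to Section 7.3.5 and a note on the tumor response form. No extra scans are needed.
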